6.2 Statistical Analysis

Prior to statistical comparison between groups (RV, RV+, and CC), all pertinent variables collected for the pilot study will be reported by groups and presented as mean, standard deviation, median, minimum, maximum and the 95% confidence intervals for continuous variables, while frequencies and proportions will be used for categorical variables. Continuous data measures will also be checked for normality and outliers. Non-normally distributed continuous data variables will be examined and transformed "normalized" if needed using appropriate transformation functions. Outliers not found to be in error will be kept in the analysis. Since the school is the randomization unit, BHS and student characteristics (Demographic and other potential confounders will be compared between the two groups using the two independent samples t-test or the non-parametric Wilcoxon signed rank test) to identify pre-treatment differences between the two groups. If the two groups are found to be statistically different in a pre-measured outcome, the pre-measurement(s) will be included in the subsequent analyses as a covariate using analysis of covariance (ANCOVA).

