6.3 Statistical Methods

Data will be analyzed using an intent-to-treat approach, wherein each participant (BHS or student) will be kept in the arm to which the school was randomized, regardless of treatment

received. In addition to creating pre/post change scores and analyzing the data using t-tests (or the Wilcoxon signed rank test), a mixed-effects model will be explored for analyzing the pre/post repeated-measures endpoints related to student academic engagement and mental health symptoms. A student-level random effect will be included and modeled using the unstructured covariance matrix to account for within-subject dependence due to repeated measurements. The models will include study arm (RTS or CC) and time of measurement (pre/post) as fixed effect. Arm x Time interaction effects will be included in the model as well. This modeling approach will allow us to compare pre-to-post changes and the extent to which these changes differ across study arms. For the purpose of generating statistical estimates for an anticipated phase 3 larger scale study, the nested nature of students within the school as well as BHS within the school will be explored using a hierarchical mixed effect multilevel model. Furthermore, we will explore marginal models using generalized estimating equations (GEE; ^{74,75}), which will produce robust estimates that adjust for clustering at the school level. Although SAS PROC MIXED will not remove participants with post-missing data from the analysis, missing data will be kept to a minimum. As a sensitivity analysis, we will impute the potential missing data using the maximum likelihood method for imputation. ⁷⁶

For the mixed-methods analyses (survey and semi-structured interview data about perceived appropriateness, feasibility, and acceptability of the training and consultation procedures, and BHS's opinions about the support they received), we will use the same data analytical approach described in IRB Protocol # 20-017895.

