8 STUDY ADMINISTRATION

8.1 Treatment Assignment Methods

8.1.1 Randomization

The 24 invited schools will be recruited from 2 geographic locations (urban/rural). Schools will be stratified based on the geographic location and a computer-generated block randomization list will be prepared to randomize the 24 schools in a 1:1:1 ratio to either RV, RV+ or CC (8 schools/arm) stratified by geographic locations (urban/rural). The block randomization with varying will ensure equal number of schools in each arm and eliminate the predictability of schools' assignment. It is estimated that a total of 72 behavioral health staff (3 staff per school- 24 per arm) and 312 students (13 students per school- 104 per arm) will participate in this randomized parallel groups pilot study.

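### Baseline becomes a covariate only after a significant baseline test, and the randomization stratum is in no model: precision may be lost and the estimator depends on the data

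*Combined protocol and SAP*

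**What the plan says.** Section 6.2 plans t-tests or Wilcoxon tests "to identify pre-treatment differences between the two groups". It continues: "If the two groups are found to be statistically different in a pre-measured outcome, the pre-measurement(s) will be included in the subsequent analyses", entering "as a covariate using analysis of covariance (ANCOVA"). The significance level is not given, and the tests named make no allowance for school, although the same sentence identifies school as the randomization unit.

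Section 6.3 gives the student analyses: "In addition to creating pre/post change scores and analyzing the data using t-tests" (or Wilcoxon), a mixed model is to be explored. Of that model it says "The models will include study arm (RTS or CC) and time of measurement (pre/post) as fixed effect", and "Arm x Time interaction effects will be included in the model as well". Hierarchical and GEE models are also to be explored, with no covariates listed.

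Section 8.1.1 describes a list to "randomize the 24 schools in a 1:1:1 ratio to either RV, RV+ or CC (8 schools/arm) stratified by geographic locations (urban/rural"). Section 3.1.1 says the same. Sections 6.2 and 6.3 do not mention the stratum.

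**The concern.** Section 6.4 says the pilot exists to estimate effect sizes, and it justifies the sample by interval width alone. Section 6.3 wants estimates to carry into a larger trial. Precision and an estimator fixed in advance are therefore what the study has to deliver.

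A baseline test is a poor switch for this purpose. Under randomization, any baseline difference is due to chance. The case for adjusting rests on how strongly the pre-score predicts the post-score, which the test does not measure. The rule can also leave one outcome analyzed by ANCOVA and another by change score, with neither choice made beforehand. The pre-scores are collected on students anyway (section 5.4), so routine adjustment costs no data.

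The baseline point concerns student outcomes only, because the documents describe no pre-measure of fidelity. The stratum point reaches both.

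**Working it through.** **1. Reproduce the plan's figure.** Section 6.4 gives 89 students per arm, an SD of 8 and a margin of 2.4.

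Half-width = t(0.975, 2n−2) × SD × √(2/n) = 1.974 × 8 × √(2/89) = 2.37.

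The stated 2.4 is therefore the unadjusted change-score half-width, with no covariate, stratum or clustering. The fidelity margins reproduce in the same way: n = 24 with SD 16 gives 9.30 (stated 9.3), and SD 0.6 gives 0.349 (stated 0.35).

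**2. Does the mixed model adjust for baseline?** Its fixed effects are arm, time and arm × time, so the arms may differ freely at baseline. With complete data the interaction estimate is (post − pre) in one arm minus (post − pre) in the other. That is the change-score difference, so the model supplies no covariate adjustment.

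**3. What routine adjustment could gain.** Let r be the pre-post correlation and k = pre SD/post SD. In units of post variance, the change score has variance 1 + k² − 2rk and ANCOVA has residual variance 1 − r².

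Variance ratio = (1 − r²)/(1 + k² − 2rk).

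The denominator minus the numerator is (k − r)², so ANCOVA is never worse (apart from the degree of freedom spent) and gains nothing when k = r. With k = 1 the ratio simplifies to (1 + r)/2. All r and k below are assumed. Half-width = 2.37 × √ratio, before clustering.

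| k | r | Ratio | Variance saving | Half-width |
|---|---|---|---|---|
| 1.0 | 0.5 | 0.75/1.00 = 0.750 | 25% | 2.05 |
| 1.0 | 0.6 | 0.64/0.80 = 0.800 | 20% | 2.12 |
| 1.0 | 0.7 | 0.51/0.60 = 0.850 | 15% | 2.18 |
| 0.8 | 0.5 | 0.75/0.84 = 0.893 | 11% | 2.24 |
| 0.8 | 0.6 | 0.64/0.68 = 0.941 | 6% | 2.30 |
| 0.8 | 0.7 | 0.51/0.52 = 0.981 | 2% | 2.34 |
| 0.7 | 0.5 | 0.75/0.79 = 0.949 | 5% | 2.31 |
| 0.7 | 0.6 | 0.64/0.65 = 0.985 | 2% | 2.35 |
| 0.7 | 0.7 | 0.51/0.51 = 1.000 | 0% | 2.37 |

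**4. What the conditional rule recovers.** This was simulated with 20,000 two-arm trials per setting, 8 schools of 11 students per arm, SD of change 8, k = 1, no clustering and baseline tests at 0.05. The SD of the estimate under change score / conditional rule / always ANCOVA was:
- r = 0.4: 1.22 / 1.16 / 1.02
- r = 0.6: 1.22 / 1.18 / 1.09
- r = 0.8: 1.20 / 1.19 / 1.14

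The rule recovers roughly a quarter of the available reduction.

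**5. How often the estimator switches by chance.** Section 6.1 lists seven student outcomes: three BASC-3 scales and four engagement scales. At level 0.05 and assuming independence, the chance that at least one switches is 1 − 0.95⁷ = 30% for one pairwise comparison. For two comparisons with control it is 1 − 0.95¹⁴ = 51%. Section 6.2 speaks of two groups in a three-arm trial, so the number of comparisons is unclear. Because the tests ignore school, the trigger rate per test rises from about 5% to about 11% at an assumed ICC of 0.05, and to 16–17% at 0.10.

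**6. Are the intervals wrong?** Without clustering, the rule's type I error was 0.043–0.047. Its coverage was 95.7% (r = 0.5) and 95.1% (r = 0.7), against 95.2% and 94.6% for always ANCOVA. At ICC 0.10, with school ignored, the rule covered about 85% and always ANCOVA 83–84%.

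**7. Stratum.** If the stratum explained 0, 5, 10 or 20% of outcome variance (assumed), the student half-width would be 2.37, 2.31, 2.25 or 2.12. The content-fidelity half-width would be 9.30, 9.06, 8.82 or 8.32.

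**The case against.** Several points on the other side stand.

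- **Baseline is not ignored.** The pre-score is always used, inside the change score or as a response in the mixed model. Only its role as a covariate is conditional.
- **The equivalence in step 2 needs complete data.** Section 6.4 expects 15% attrition, and section 6.3 says the mixed model keeps students without a post score. The estimates will then differ somewhat. The baseline arm means remain unconstrained, however, so the adjustment is still missing.
- **The gain may be small.** Students are selected for elevated screening scores (sections 3.1.1 and 3.3.1), so a narrower spread before treatment than after (k below 1) is plausible. The equal-SD rows correspond to about 33%, 25% and 18% more students (1/0.75, 1/0.80, 1/0.85). A reader might take that as the cost of the present rule, but it depends on equal SDs, which the documents do not establish.
- **The stratum may matter little.** Sections 3.1.1 and 8.5 direct recruitment to schools in rural or town areas or serving rural communities, so the urban stratum may be small or empty. Leaving out a stratification factor tends to make inference conservative.
- **The setting is modest.** This is an unpowered pilot, the models beyond the t-tests are exploratory, and section 6 says the SAP will be updated before database lock. It does not promise this change.

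A reader might also infer that choosing the model by a pre-test makes the 95% intervals invalid. Step 6 does not support that: overall coverage is near nominal without clustering. The shortfall at ICC 0.10 comes from ignoring school, which is a separate issue that baseline adjustment does not cure.

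**Conclusion.** The point holds as one of efficiency and prespecification, and it should be fixed. Covariate adjustment for baseline depends on a significance test that ignores school, the fallback analyses do not supply that adjustment, and the stratum is in no model. The consequences are lost precision and an estimator that can change from outcome to outcome.

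Over the settings tabulated, the variance saving from always adjusting runs from 0% to 25%, which takes the student half-width from 2.37 to between 2.37 and 2.05 before clustering. This rests on assumed r and k. The switching probabilities assume independent tests at 0.05, and the trigger rates above 5% assume an ICC. The stratum's gain cannot be derived from the documents and may be nil; the reason to include it is that the analysis should reflect how schools were allocated. Neither invalid intervals overall nor a guaranteed large saving follows from the documents.

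**What to change.** In the SAP, before database lock:

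1. Delete the baseline significance tests and the conditional ANCOVA rule from section 6.2. Keep the descriptive baseline summaries by arm.
2. In every student outcome model, prespecify adjustment for that outcome's own baseline value, whatever the observed imbalance. Use ANCOVA, or a longitudinal model with baseline means constrained equal across arms, which keeps students with a missing post score. Fit it within a model that accounts for school.
3. Include the urban/rural stratum as a fixed effect in the student and fidelity models if both strata are filled, and state what will be done if one is empty.

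The cost is SAP wording and no new data. The stratum takes one degree of freedom: at school level, with 24 schools and three arms, 24 − 3 = 21 becomes 20.

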6.3 Statistical Methods

Data will be analyzed using an intent-to-treat approach, wherein each participant (BHS or student) will be kept in the arm to which the school was randomized, regardless of treatment

received. In addition to creating pre/post change scores and analyzing the data using t-tests (or the Wilcoxon signed rank test), a mixed-effects model will be explored for analyzing the pre/post repeated-measures endpoints related to student academic engagement and mental health symptoms. A student-level random effect will be included and modeled using the unstructured covariance matrix to account for within-subject dependence due to repeated measurements. The models will include study arm (RTS or CC) and time of measurement (pre/post) as fixed effect. Arm x Time interaction effects will be included in the model as well. This modeling approach will allow us to compare pre-to-post changes and the extent to which these changes differ across study arms. For the purpose of generating statistical estimates for an anticipated phase 3 larger scale study, the nested nature of students within the school as well as BHS within the school will be explored using a hierarchical mixed effect multilevel model. Furthermore, we will explore marginal models using generalized estimating equations (GEE; ^{74,75}), which will produce robust estimates that adjust for clustering at the school level. Although SAS PROC MIXED will not remove participants with post-missing data from the analysis, missing data will be kept to a minimum. As a sensitivity analysis, we will impute the potential missing data using the maximum likelihood method for imputation. ⁷⁶

For the mixed-methods analyses (survey and semi-structured interview data about perceived appropriateness, feasibility, and acceptability of the training and consultation procedures, and BHS's opinions about the support they received), we will use the same data analytical approach described in IRB Protocol # 20-017895.

The statistical analysis related to the secondary aims to examine the mediators and moderators effects of consultation support on behavioral health staff fidelity will utilize PROCESS⁸⁵ a modeling tool freely-available for SPSS and SAS. The many features of PROCESS integrate many existing functions and published statistical tools for analyzing mediation and moderation. The SAS software ⁸³; and the SPSS software ⁸⁴ will be utilized for data analyses. The qualitative examination of school staff's perceived feasibility, appropriateness and acceptability of the support they received will be in NVivo and analyzed thematically.

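### Schools are randomised, but no school-adjusted analysis is designated as the main one, so the pilot's own confidence intervals for arm differences are liable to be too narrow

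*Combined protocol and SAP*

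**What the plan says.** All references are to the combined protocol and SAP.

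- **Allocation.** Section 6.2 begins a sentence "Since the school is the randomization unit". Section 8.1.1 says that "a computer-generated block randomization list will be prepared to randomize the 24 schools in a 1:1:1 ratio to either RV, RV+ or CC", with 8 schools per arm. It expects 13 students and 3 staff per school, or 104 students and 24 staff per arm.
- **Analyses without school.** Section 6.3 has pre/post change scores compared by t-test or Wilcoxon test. This is the only comparison stated without hedging. It then offers, as something to be explored, a mixed model for the student endpoints: "A student-level random effect will be included and modeled using the unstructured covariance matrix to account for within-subject dependence". The fixed effects are arm, time and their interaction.
- **Analyses with school.** In a sentence about producing estimates for a later phase 3 study, Section 6.3 says "the nested nature of students within the school as well as BHS within the school will be explored" with a hierarchical model, whose random terms are not listed. GEE models, "which will produce robust estimates that adjust for clustering at the school level", are also to be explored.
- **Mediation and moderation.** Section 6.3 names PROCESS, "a modeling tool freely-available for SPSS and SAS", and does not say how staff nested within schools will be handled.
- **Precision.** Section 6.4 gives 95% margins of error of 2.4 (student change), 9.3 (content fidelity) and 0.35 (process fidelity). It gives no ICC or design effect, and says the pilot is not powered for specific hypotheses.
- **Fidelity measurement.** Under Section 5.3 the CI/CO content checklist is completed once, from the school's own manual. Section 6.1 makes content fidelity a primary endpoint.

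**The concern.** When schools are allocated, each arm contrast rests on 8 schools against 8. Students in one school share the group programme their school selected (Section 3.1) and may share the teachers who rate engagement (Section 5.4). Outcomes within a school are therefore likely to be correlated. An analysis that treats students as independent then understates the standard error of the arm difference.

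Section 6.3 lists four candidate analyses for the student endpoints and ranks none of them. The one stated firmly ignores school, so an analyst could follow the plan exactly and report that result. Section 6.4 describes the pilot's product as effect estimates with 95% intervals. Intervals that are too narrow damage that product directly.

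**Working it through.** **Inputs.** From Section 6.4: 89 evaluable students per arm with SD of change 8; 24 staff per arm with SD 16 (content) and 0.6 (process); two-sided 95%. From Section 8.1.1: 8 schools per arm. So m = 89/8 = 11.125 students, or 24/8 = 3 staff, per school. The ICC is not in the documents and is assumed to lie between 0.01 and 0.20. For students it is the ICC of the change score.

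**Step 1: reproduce the plan's margins, assuming independence.** Half-width = t(0.975, 2n-2) x SD x sqrt(2/n).

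- Student: 1.974 x 8 x sqrt(2/89) = 2.37 (stated 2.4)
- Content fidelity: 2.013 x 16 x sqrt(2/24) = 9.30 (stated 9.3)
- Process fidelity: 2.013 x 0.6 x sqrt(2/24) = 0.349 (stated 0.35)

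All three match with a design effect of exactly 1.

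**Step 2: allow for school.** DE = 1 + (m-1) x ICC. Half-width = t(0.975, 14) x SD x sqrt(2/n x DE), with 14 df from the 16 schools in a pairwise contrast. Type I error is for an individual-level t-test at nominal 5%, simulated under the null with 8 schools per arm and 11 students per school (40,000 runs per row).

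| Assumed ICC | DE | Effective n per arm | Student half-width | Type I error |
|---|---|---|---|---|
| 0.01 | 1.10 | 81 | 2.70 | 6.2% |
| 0.02 | 1.20 | 74 | 2.82 | 7.3% |
| 0.05 | 1.51 | 59 | 3.16 | 11.0% |
| 0.10 | 2.01 | 44 | 3.65 | 16.7% |
| 0.20 | 3.03 | 29 | 4.47 | 25.9% |

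With ICC 0 the half-width on 14 df is already 2.57, so part of the widening comes from the degrees of freedom. Repeat simulations of 20,000 runs gave 7.4-7.6%, 10.6-10.8% and 16.3-16.9% at ICC 0.02, 0.05 and 0.10. A t-test on school means stayed at about 5% throughout.

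**Step 3: staff, 3 per school.** At ICC 0.05, 0.10 and 0.20 the content margin is 10.4, 10.9 and 11.7, and the process margin is 0.39, 0.41 and 0.44. Type I error is 6.3%, 7.4% and 9.4%. At ICC 0.01 it is 5.1%.

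CI/CO content fidelity is a special case. Sections 3.2.1 and 4.3 put two of the three staff in each school on CI/CO. If both carry the school's single score, an arm has 8 group implementers plus 8 school scores = 16 distinct values, not 24.

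**Step 4: the student-only mixed model.** With complete pre/post data its arm-by-time test is equivalent to the change-score t-test, so it has the same error.

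**Step 5: which school term is needed.** Let Y(t) = fixed effects + school + student + error(t). Then Y(post) - Y(pre) contains neither the school nor the student effect, because both are constant over time. A school intercept therefore leaves the arm-by-time standard error unchanged. Numerically, with SD 1 and 88 students per arm, it is sqrt(2/88) = 0.1508 with or without the intercept. Only a school-by-time effect, or a school intercept in a model for change or for baseline-adjusted post scores, widens it.

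**Step 6: GEE.** If an uncorrected sandwich variance were used with a normal reference and 16 schools, simulated type I error is about 8-9% at every ICC tried.

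**The case against.** The best defence is that the plan does recognise clustering: it names a school-nested model and school-clustered GEE. The trial is also an estimation pilot, and the opening of Section 6 says the SAP will be updated and finalised before database lock. All of this is true. It makes interval width, rather than the false-positive rate, the main issue, and it makes the repair easy. It does not settle which result will be reported.

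Several stronger readings are tempting but not supported:

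- A reader might take the student-only model as a firm commitment. Section 6.3 calls it exploratory too; only the t-test/Wilcoxon comparison is unhedged.
- A reader might conclude that the phase 3 estimates will be spuriously precise. Section 6.3 links those estimates to the school-nested model. The intervals at risk are those in the pilot's own report.
- A reader might infer that the GEE standard errors are uncorrected, or that the PROCESS models omit school. The documents specify neither the variance estimator nor the model terms, so these are gaps to fill rather than stated errors.
- A reader might apply the student figures to staff. The t-test sentence is tied to pre/post change scores, the only model naming staff nests them in schools, and with 3 per school the inflation is modest.
- A reader might blame shared trainers and raters. Training and consultation come from central research staff, and the BASC-3 scales are described as parent-reported. Programme choice and teacher-rated engagement are the more plausible sources.

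**Conclusion.** The point stands in this form: the unit of randomisation is the school, the only firmly stated comparison ignores it, and no school-adjusted analysis is designated as the main one. At an assumed ICC of 0.05 the student interval should be about a third wider than planned (3.16/2.37 = 1.33). At 0.10 it should be about half as wide again (3.65/2.37 = 1.54).

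The direction holds for any positive ICC. The size depends on an ICC the documents do not supply, and on equal school sizes and normal outcomes in the simulation. At ICC 0 the type I error of the individual-level t-test is about 5%. For staff the effect is negligible at ICC 0.01 and reaches roughly 9-10% type I error at 0.20, apart from CI/CO content fidelity, where dependence is built into the measurement.

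**What to change.** Before database lock, amend Sections 6.3 and 6.4 to:

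1. Designate a school-adjusted analysis as the main one for every quantitative arm contrast.
2. For student endpoints, use a change-score or baseline-adjusted (ANCOVA) model with a random school intercept. Alternatively, use a pre/post model with a school-by-time random effect as well as school and student effects. State that a school intercept alone is not sufficient for the arm-by-time contrast.
3. For staff fidelity, use a random school intercept. Analyse CI/CO content fidelity at school level.
4. Use small-sample degrees of freedom (Kenward-Roger is one option). Run any t-tests on school means. If GEE is reported, name a small-sample variance correction.
5. State how school is handled in the mediation and moderation analysis, for example with a multilevel model or a bootstrap that resamples schools.
6. Restate the margins over a range of ICCs, as in the table above.

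The cost is SAP wording, a few lines of SAS, and wider intervals. No change to design or data collection is needed.

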2 STUDY OBJECTIVES

2.1 Primary Objective (or Aim)

The purpose of this study is to conduct a pilot randomized controlled trial comparing three training strategies: Control Condition (CC), Remote Video (RV), and Remote Video plus Coaching (RV+).

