6.4 Sample Size and Power

The proposed pilot study aims to collect data and estimate effect sizes measuring the effect of RV and RV+ when compared to the CC. Although, this pilot study is not powered to test for specific hypotheses regarding effect sizes, the sample size estimates were based on data obtained from our recently completely NIH funded study, ^{15,77} we estimated that a total of 72 BHS (24 per arm) and 312 students will participate in this study. With 24 BHS per arm, a two-sided 95% confidence interval in mean differences in content fidelity (CF) and process fidelity (PF between) RV or RV+ vs. CC will be produced. The minimum distance from the mean difference to the limits (margins of error) will equal to 9.3 (CF) and 0.35 (PF) with the estimated pooled standard deviations equal to 16 and 0.6 respectively. It is anticipated that 104 students per arm will be recruited (total = 312). Assuming a uniform attrition rate of 15%, a total of 268 evaluable students will be included in the final statistical analysis. With 89 students in each of the three study arms, a two-sided 95% confidence interval for mean differences in pre/post changes in student mental health symptoms and academic engagement between the two arms ((RV or RV+) vs. CC) will equal to 2.4 with estimated

pooled standard deviation equal to 8. Sample size justification was reported using PASS 13 software.⁷⁸

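### Sections 6.2 and 6.3 are worded for two groups in a three-arm trial and conflict with section 6.4; RV+ versus RV is not specified; and a paired rank test is named where arms are compared

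*Combined protocol and SAP*

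**What the plan says.** **Design and objective.** Section 8.1.1 will "randomize the 24 schools in a 1:1:1 ratio to either RV, RV+ or CC (8 schools/arm"), and the primary objective in section 2.1 is a comparison of all three strategies.

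**Section 6.2.** It opens with three groups: "Prior to statistical comparison between groups (RV, RV+, and CC"). It then refers three times to two groups. Baseline characteristics are to be "compared between the two groups using the two independent samples t-test or the non-parametric Wilcoxon signed rank test".

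**Section 6.3.** Pre/post change scores are formed, with the plan "analyzing the data using t-tests (or the Wilcoxon signed rank test"). The type of t-test is not stated. In addition, a mixed-effects model is to be explored for the student endpoints: "The models will include study arm (RTS or CC) and time of measurement (pre/post) as fixed effect". An Arm x Time interaction is included, and the stated purpose is to compare changes across the study arms. RTS is not in the abbreviation list. The nearest phrase is the Remote Training Strategy of section 3.1.1.

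**Section 6.4.** The pilot is to "estimate effect sizes measuring the effect of RV and RV+ when compared to the CC". Margins of error are given for RV or RV+ against CC: 9.3 for content fidelity, 0.35 for process fidelity and 2.4 for student change.

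**The concern.** The arm factor in the student model has two levels, while the trial has three arms. Whoever programs section 6.3 must decide what RTS is. The natural reading, Remote Training Strategy, covers both RV and RV+ and merges them. The merged contrast is not what section 6.4 plans, and it hides any difference between the remote arms. Remote coaching and consultation (section 4.3.1) are what RV+ adds to RV. A secondary objective (section 2.2) concerns consultation support, and section 6.3 wants estimates for a larger trial. A blended effect serves neither purpose well. If the wording stays, the choice between pooled and separate arms could be made after the data are seen.

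The rank test is a second problem. The signed rank test needs pairs or a single sample, so it cannot compare independent arms. Applied within an arm, it asks whether that arm changed. Students enter because they score at least 1 SD above the mean on an SDQ scale (section 3.3.1), so some improvement in every arm can be expected from regression to the mean alone.

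**Working it through.** **1. Reproduce the section 6.4 margins.** Inputs from section 6.4: two-sided 95% intervals; 24 staff per arm with SD 16 (content fidelity) and 0.6 (process fidelity); 89 students per arm with SD 8. For two separate arms of size n:

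half-width = t(0.975, 2n − 2) × SD × √(1/n + 1/n)

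- Content fidelity: 2.013 × 16 × √(2/24) = 9.297 (stated 9.3)
- Process fidelity: 2.013 × 0.6 × √(2/24) = 0.349 (stated 0.35)
- Students: 1.974 × 8 × √(2/89) = 2.367 (stated 2.4; with 88 per arm it is 2.380)

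All three agree after rounding.

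**2. Margins if RV and RV+ are pooled.** The comparison becomes 2n against n:

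half-width = t(0.975, 3n − 2) × SD × √(1/(2n) + 1/n)

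**3. Margins from a three-level arm factor.** Pooled variance with 3n − 3 degrees of freedom, for each pairwise contrast.

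| Endpoint | Stated in 6.4 | Separate arms | Three-level factor | RV and RV+ pooled |
|---|---|---|---|---|
| Content fidelity | 9.3 | 9.297 | 9.21 | 7.98 |
| Process fidelity | 0.35 | 0.349 | 0.346 | 0.299 |
| Student change | 2.4 | 2.367 | 2.36 | 2.04 |

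The stated margins therefore fit only arms kept apart. All these figures ignore clustering by school, as section 6.4 does. The fidelity rows serve only to identify which comparison section 6.4 assumed, because the RTS/CC model covers student endpoints alone.

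**4. What a pooled coefficient estimates.** Let the effects against CC be a (RV) and b (RV+). With equal numbers in the two arms, the pooled coefficient is (a + b)/2. Illustrative values, not from the plan:

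- a = 0, b = D gives D/2; for example, 0 and 4 give 2.
- a = 2, b = 4 gives 3.
- a = −2, b = 4 gives 1.

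One coefficient cannot recover a, b or b − a.

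**5. The signed rank test.** A simulation of 4,000 runs used 89 students per arm and SD 8, with an assumed 4-point improvement in both arms and no difference between them. The signed rank test within one arm rejected in 99.5% of runs. The rank-sum test between arms rejected in 5.0%, its nominal level. The first answers whether an arm changed, the second whether arms differ. Forcing the signed rank test across arms would need an arbitrary pairing. In one simulated data set with an assumed 3-point difference, p ran from 0.0003 to 0.032 over 1,000 random row orders, and the test could not be run at all with 89 against 88.

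**The case against.** The strongest reply is that this is a leftover label. RTS is undefined, section 6.2 opens with all three groups, section 6.3 keeps participants in the arm to which their school was randomised, and section 6.4 commits to RV and RV+ each against CC. Two-sample t-tests on change scores could supply those two contrasts without the mixed model. The model itself is only to be explored, and it covers student endpoints, not fidelity. The study is a pilot that section 6.4 says is not powered for specific hypotheses, and section 6 says the analysis plan will be finalised before database lock.

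Most of this stands, and it rules out several stronger inferences:

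- A reader might infer that the trial will not produce its contrasts with CC. Section 6.4 commits to them; it is the model as worded in section 6.3 that cannot deliver them.
- A reader might infer that section 6.2 recognises only two groups. Its first sentence names three.
- A reader might infer that the sponsor decided to pool, so that halving of an RV+ effect is established. Pooling rests on one reading of an undefined term, and halving also needs RV to have no effect.
- A reader might infer that RV+ versus RV is the plan's declared target. Section 2.1 makes it a reasonable request, but section 6.4 names only contrasts with CC.
- A reader might infer that the signed rank test in section 6.3 is an error under any reading, or that regression to the mean would decide the trial's conclusions. On change scores within an arm the test is valid, and the Arm x Time term compares change between groups. The plain error is in section 6.2, where the test serves a baseline comparison.

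The reply does not remove the conflict. Sections 6.3 and 6.4 cannot both be followed as written, and no between-arm rank test is named anywhere.

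**Conclusion.** Wrong as written, and correctable by wording alone. The two-level arm factor in section 6.3 and the two-group tests in section 6.2 conflict with the three-arm randomisation, the objective and section 6.4. Taken literally, with RTS read as Remote Training Strategy, the student model estimates the average of the RV and RV+ effects. It would carry a margin of about 2.04 where section 6.4 plans 2.4, and it would give none of RV−CC, RV+−CC or RV+−RV. The size of any distortion depends on how far RV and RV+ differ, which the documents do not say. RV+ versus RV is specified nowhere in section 6. The signed rank test is the wrong alternative in section 6.2; in section 6.3 it can test only change within an arm. The section 6.4 figures are sound on this point.

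**What to change.** - **Section 6.3, model:** define study arm as a three-level factor (CC, RV, RV+) with Arm x Time. Define RTS or delete it.
- **Section 6.3, contrasts:** list RV−CC and RV+−CC, and add RV+−RV as the added effect of coaching, each with a 95% confidence interval.
- **Section 6.3, change scores:** say whether the tests are within or between arms. Where arms are compared, use the two-sample t-test or the Wilcoxon rank-sum test for each named pair, or Kruskal-Wallis for three arms. Keep the signed rank test, if wanted, only for change within an arm and label it so.
- **Section 6.2:** change two groups to three throughout, and replace the signed rank test in the same way.
- **Section 6.4:** no change on this ground.

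The cost is wording in the protocol and analysis plan before database lock, with no new data and no change in sample size. A three-level factor gives pairwise margins of 9.21, 0.346 and 2.36, so the planned precision is kept on the plan's own assumptions. Whether these tests and intervals allow for clustering by school is a separate issue and is not settled by this change.
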